4.2. Age groups

Age groups will be defined for the analysis on basis of the actual age distribution of the study population, ensuring reasonable group sizes as well as medically meaningful age ranges. These ranges will be decided during the data review process preceding the database (DB) lock. All data will be presented by these age groups as appropriate, as well as for all patients overall.

4.3. Selection of Study Population

The study population consists of pediatric patients of both sexes who need TPE. Please refer to the protocol, section 4.1 for a complete list of inclusion and exclusion criteria.

9/21

5. Sequence of Planned Analyses

5.1. Interim Analyses

No interim analysis is planned.

5.2. Final Analyses and Reporting

The purpose of this study is to assess safety and tolerability of octaplas™ in the pediatric population by monitoring SAEs, ADRs, TEs, TEEs, and by measuring safety laboratory parameters. No confirmatory testing is planned, but all data collected will be explored and presented descriptively in full detail, by age group as well as in total, to facilitate the review of population homogeneity and general patterns within and between the age groups. Any p-value or confidence interval presented is to be understood in the exploratory sense.

To facilitate the detection of any possible safety signal, all SAEs, ADRs, TEs, and TEEs will be characterized and analyzed by seriousness, severity, relation to study drug and timely relationship to study drug administration. In addition to these pre-planned categories the collected data will be examined to identify additional characteristics of interest such as particular indications for TPE, relevant concomitant medications, or SMQs covering a noticeable number of events. The rates of SAEs, ADRs, TEs, and TEEs will be presented for all these categories, together with the associated 95% confidence intervals, again per age group and in total.

Individual patient profiles or tabulations will be generated, displaying the baseline characteristics as well as all interventions, treatment details and measurements on a time scale. This will facilitate the review of each individual course of treatment by a medical expert to detect any safety signal that might not be reflected in the event rates.

6. Sample Size Determination

A minimum of forty (40) pediatric patients aged \geq 2 years to \leq 20 are planned to be enrolled into this study. The chosen number of 40 pediatric patients is not derived from statistical considerations of power, but to gather enough clinical evidence to obtain a sound and meaningful medical assessment.

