9 STATISTICAL METHODS AND SAMPLE SIZE

9.1 Determination of Sample Size

A minimum of 40 pediatric patients are planned to be enrolled.

The purpose of this study is to assess safety and tolerability of octaplasTM in the pediatric population by monitoring ADRs and safety laboratory parameters. The sample size of at least 40 pediatric patients is not derived from statistical considerations of power, but to gather enough clinical evidence to obtain a sound and meaningful medical assessment for patients ≥ 2 and ≤ 20 years of age.

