6 ADVERSE REACTIONS

Serious adverse reactions seen in clinical trials were anaphylactic shock, citrate toxicity and severe hypotension.

The most common adverse reactions observed in $\geq 1\%$ of subjects included pruritis, urticaria, nausea, headache, and paresthesia.

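### Reaction groups get a 95% CI only if their observed count is noticeable, so most of the label's key reactions have no guaranteed reaction-specific upper limit

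*SAP*

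**What the plan says.** SAP 5.2 fixes four ways of classifying events in advance. SAEs, ADRs, TEs and TEEs will be "characterized and analyzed by seriousness, severity, relation to study drug and timely relationship to study drug administration". None of these is a specific reaction. Further categories come from inspection: "the collected data will be examined to identify additional characteristics of interest such as particular indications for TPE". Other medicines given alongside are a second example, and the one that concerns reaction groups is "or SMQs covering a noticeable number of events". Rates of the four event classes are then given for all these categories, "together with the associated 95% confidence intervals, again per age group and in total". Protocol 9.2 and the protocol synopsis use the same selection wording, applied to ADR rates. Neither document puts a number on noticeable, lists SMQs or preferred terms in advance, or names a CI method.

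SAP 11.1 separately gives the number and percentage of patients by system organ class and preferred term. It sets no count threshold and mentions no CI.

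The package insert (protocol Appendix 1, section 6) states: "Serious adverse reactions seen in clinical trials were anaphylactic shock, citrate toxicity and severe hypotension". Its sections 5.2 to 5.5 warn of hypervolemia, hyperfibrinolysis, thrombosis and citrate toxicity.

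On size, SAP section 6 plans for "A minimum of forty (40) pediatric patients aged" 2 to 20 years, a number that "is not derived from statistical considerations of power, but to gather enough clinical evidence". Protocol 9.1 gives the aim as "to gather enough clinical evidence to obtain a sound and meaningful medical assessment for patients" in that age range. No precision or upper limit is stated.

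**The concern.** Whether a reaction group receives an interval depends on that group's own count, judged after the data are seen. This has two consequences.

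First, a rare serious reaction is the kind most likely to be seen in no child or one child out of 40, and so to miss the threshold. For such a reaction the upper limit is the informative number. Without it, the report could say that anaphylaxis or citrate toxicity was not observed and leave unsaid what rate the data still allow. The study is a required pediatric safety assessment, and section 8.4 of the insert says safety has not been evaluated in children.

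Second, a group displayed because its count was high has, on average, an observed rate above its true rate. An interval around that rate inherits the shift.

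**Working it through.** **Inputs.** N = 40 (SAP section 6, a minimum) and confidence level 95% (SAP 5.2). The following are assumptions, because the documents do not give them: two-sided exact (Clopper-Pearson) limits; a display threshold of k = 1, 2 or 3 children; true reaction rates of 1% to 10%; age groups of 20 or 10 (SAP 4.2 leaves the groups to the data review); each child counted once, with or without the reaction. The plan has no precision figure of its own to reproduce.

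**1. Which reactions already have an interval.** SAP 5.2 covers SAE, ADR, TE and TEE. Thrombosis and thromboembolism therefore have one. Hypersensitivity/anaphylaxis, citrate toxicity/hypocalcaemia, hypotension, circulatory overload and bleeding/hyperfibrinolysis have one only if selected.

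**2. What a zero count allows.** Upper limit = 1 − 0.025^(1/N).
- 0/40: 1 − 0.025^(1/40) = 8.8%
- 0/20: 1 − 0.025^(1/20) = 16.8%
- 0/10: 1 − 0.025^(1/10) = 30.8%

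A zero count is likely for a rare reaction. P(X = 0) = (1 − p)^40, which is 66.9% at p = 1% and 44.6% at p = 2%.

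**3. Whether the overall serious-event interval fills the gap.** Its upper limit also bounds each single serious reaction. For an assumed 5/40 children with any serious event, the exact upper limit is the 97.5% quantile of Beta(6, 35) = 26.8%, against 8.8% for a specific reaction at 0/40. The two agree only if no child has any serious event.

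**4. Selection on the count.** With X ~ Binomial(40, p), a group is displayed with its CI if X ≥ k. The mean displayed rate is E[X/40 | X ≥ k]. For k = 1 this is p / P(X ≥ 1); at p = 2%, 0.02 / 0.554 = 3.61%.

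| True rate | k = 1: chance selected; mean shown (ratio) | k = 2 | k = 3 |
|---|---|---|---|
| 2% | 55.4%; 3.61% (1.8) | 19.0%; 5.73% (2.9) | 4.6%; 8.02% (4.0) |
| 5% | 87.1%; 5.74% (1.15) | 60.1%; 7.19% (1.44) | 32.3%; 9.08% (1.82) |
| 10% | 98.5%; 10.15% (1.02) | 92.0%; 10.70% (1.07) | 77.7%; 11.74% (1.17) |

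Coverage of the exact 95% CI among displayed groups suffers mainly when the reaction is rare and the threshold high. At a true 2% it is 98.5%, 95.7% and 82.0% for k = 1, 2 and 3. At a true 5% it stays between 95.7% and 98.4%.

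**The case against.** The plan reports more than the SMQ sentence suggests, and most of this case stands as a limit on the point.

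- A reader might infer that a rare reaction would rarely be shown at all, taking the 4.6% above as its chance of appearing. The documents do not support that. One case is enough to enter the SAP 11.1 listings and incidence tables, and SAP 3.2.1 also promises rates per patient and per TPE for relevant combinations of characteristics. The 4.6% applies only to the selected display with its CI, under k = 3.
- A reader might infer that serious reactions have no upper bound. The unconditional serious-event interval is one, though loose.
- A reader might infer a zero-width interval at 0/40 from a normal approximation. No CI method is named, so nothing supports that prediction.
- Citrate effects and blood pressure are followed directly. Ionized calcium is a secondary endpoint with abnormal flags (SAP 11.2), out-of-range vital signs are reviewed individually (protocol 9.2.3), and each serious event gets a narrative (SAP 11.1). This supports clinical review but gives no reaction rate with an interval.
- All CIs are exploratory, and SAP section 2 already requires unplanned analyses to be identified. Data-chosen groups therefore need not lose their CIs. The exploratory label does not remove the selection effect.
- The table list is deferred to a separate document, which may name reaction groups. The SAP text does not require it to.
- A reader can work out a 0/N limit from the reported N. That is true, but a planned safety assessment should not depend on it.

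**Conclusion.** The point holds in a limited form. The gap is the reaction-specific interval and the zero-count row for five label-derived groups; it does not extend to the visibility of events that occur, or to thrombosis. At the minimum enrolment, a reaction seen in no child remains compatible with a rate of up to 8.8%, and the plan does not commit to saying so. The upward shift in selected groups is material for rare reactions (1.8 to 4.0 times a true 2%), moderate at 5% (1.15 to 1.82 times) and small at 10% (1.02 to 1.17 times). Its actual size cannot be fixed, because it depends on an undefined threshold and on true rates that the documents do not give. The study remains interpretable without the change, but the change should be made because it is cheap and supports the assessment that protocol 9.1 promises.

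**What to change.** Before database lock:

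- In SAP 5.2 and 11.1, list the groups by MedDRA definition: hypersensitivity/anaphylaxis, citrate toxicity/hypocalcaemia, hypotension, circulatory overload, bleeding/hyperfibrinolysis. For each, report the number of children with at least one event as x/N with the exact (Clopper-Pearson) 95% CI, including x = 0, overall and by age group.
- Label any group added after looking at the data as post hoc. It may keep its CI.
- In SAP section 6 and protocol 9.1, state that with the minimum of 40 patients a zero count has an exact two-sided 95% upper limit of 8.8%, and give the limits for the age-group sizes once these are known (16.8% for 20, 30.8% for 10, if those sizes arise).

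The cost is some wording and one more table, with no change to conduct, data collection or sample size. The downside is that the stated precision looks less favourable, especially by age group.

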6.1. Patient Replacement Policy

There is no patient replacement policy defined for this protocol. The number of withdrawals and the actual age distribution of the study participants will be monitored in order to define appropriate age groups for the data analysis prior to DB lock.

6.2. Premature Termination of the Study

If early termination of the study becomes necessary for whatever reason, the sponsor and the investigator will ensure that adequate consideration is given to the protection of the patients' interests. Such a premature termination will be communicated in accordance with applicable regulatory requirements. The Investigator will promptly inform the Independent Ethics Committee (IEC)/Institutional Review Board (IRB) and provide a detailed written explanation. The pertinent regulatory authorities will be informed according to national regulations.

7. Analysis Populations

The following populations will be considered for the statistical analysis:

The safety population (SAF) will include all patients who received at least one infusion of octaplas.

The full analysis set (FAS) is defined according to the intent-to-treat (ITT) principle and will include all patients of the SAF with any information available on the primary endpoint; these are all treated patients monitored for the above mentioned events (SAEs, ADRs etc.) after start of the TPE, and it is thus expected that this population will coincide with the SAF.

The per-protocol (PP) population will include all patients who have completed the infusion episode(s) and the final examination without major protocol deviations that would have an effect on the evaluation of the primary endpoint. Examples of protocol deviations to be considered in this respect would be violations of the study entry criteria, dosing errors, the use of prohibited concomitant medications, or the occurrence of completely unrelated medical events that require an interruption of the study procedures. The final decision regarding inclusion/exclusion of patients from the analysis sets will be taken by a panel including the Clinical Project Manager, the study statistician and a medical expert during a data review meeting before database lock. The decisions taken will be based on a review of complete data listings, and documented before the database is locked and the analysis is performed.

8. General Issues for Statistical Analysis

Descriptive summaries will be presented for each of the primary and secondary variables. In general, summaries will be completed for all patients overall and by age group. Continuous, quantitative variable summaries will include the number of patients with non-missing values (N), mean, standard deviation, median, minimum and maximum, 1st and 3rd quartile.

Categorical, qualitative variable summaries will include the frequency and percentage of patients who are in the particular category. In general the denominator for the percentage calculation will be the total number of patients in the analysis population unless otherwise specified.

8.1. Analysis Software

Statistical analyses will be performed using SAS Software version 9.1 or later.

8.2. Withdrawals

Patients who withdraw from the study prematurely will be considered in all data presentations for which they contribute data.

A list of all withdrawals and the reasons of withdrawal will be included in appendix 16.2 of the CSR.

8.3. Handling of Missing Data

In general, missing data will not be imputed; for calculations concerning the body weight, in particular the administered doses per kg, the latest available body weight measurement will be used.

No analyses of the patterns of missing data will be done.

For medications the following will be applied: A medication will be assumed to be concomitant if it can be definitely shown that the medication was administered after start of the first octaplas infusion and before the end of the observation period. Missing dates will not be replaced.

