4.2 Prior and Concomitant Therapy

Details of relevant concomitant medications will be recorded in the CRF. Relevant medications are defined as follows:

- Plasma products (e.g., octaplasTM, regular plasma products, etc.) and all other blood products that are administered.
- Antifibrinolytics (ε-aminocaproic acid or tranexamic acid) and any other pharmaceutical pro- or anti-coagulants such as recombinant activated factor VII (rFVIIa), any of the prothrombin complex concentrates, or fibrinogen concentrates.
- Pre-transfusion medications taken to prevent allergic reactions (including steroids)
- An angiotensin-converting-enzyme (ACE) inhibitors (Lisinopril, Captopril, etc.)
- Other medications that the Investigator considers relevant to report for this trial.

Routine medications that are considered standard and/or that have little or no impact on the study data results are not to be entered into the CRF. Relevant concomitant medications or changes thereof must be recorded. If the change influences the patients' eligibility to continue in the trial, the Sponsor must be informed.

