5.4 Dose and Dosing Schedule

octaplasTM, ABO blood group specific, will be given as replacement fluid during TPE and administered per institutional standard of care. It will be used in lieu of FFP during the treatment period.

The total octaplasTM volume infused and time details of each infusion episode will be recorded.

Patients will be followed for one week (7 days) during their therapy which could consist of one or more TPE procedures. The recommended dose is a total plasma volume between 40 to 60 mL/kg, as prescribed by the treating physician. The dosing regimen might differ from the general recommendation, depending on the therapeutic treatment plan and the investigator's evaluation of the respective clinical situation (e.g. plasma exchange). The infusion rate of octaplasTM should not exceed 0.020-0.025 mmol/kg BW (body weight)/min, which is equal to <1 mL/kg BW/min.

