6.2 Duration of Study

6.2.1 Planned Duration for an Individual Patient

Treatment up to one week (7 days) maximum will be documented. 24 hours (+/- 2 hours) after the last TPE, the final follow-up will be performed to identify and record any SAEs, ADRs, TEs,

³ At least one blood sample should be drawn within 90 minutes after start of each TPE. All subsequent samples should also be reported in the CRF.

TEEs, as well as concomitant medications and Investigator's overall safety assessment. This visit will also be the study completion visit.

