9.3. Demographics and Other Baseline Characteristics

Descriptive summaries of the demographic and other baseline characteristics will be completed for the populations specified below, overall and by age group; these include:

 Demographics (Age, Gender, Race/Ethnicity, Height, Weight, BMI (calculated), ABO blood group)

(SAF, FAS, PP)

Medical History (SAF)

Medical history will be coded with the Medical Dictionary for Regulatory Activities (MedDRA, according to the version specified in the Data Management Plan). Incidences of findings in medical history will be summarized by MedDRA system organ class (SOC) and preferred term (PT)

Prior and Concomitant Medications (SAF)

Medications will be coded using the WHO Drug Dictionary (according to the version specified in the Data Management Plan). Incidences of prior and concomitant medications will be summarized by ATC level 2 and ATC level 4

Baseline Physical Examination, including vital signs (SAF)

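### Does the SAP's rule for calling a drug concomitant need rewriting because it passes over premedication before the first infusion and drugs of uncertain timing?

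*SAP*

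**What the plan says.** SAP section 8.3 treats a drug as "assumed to be concomitant if it can be definitely shown that the medication was administered after start of the first octaplas infusion", provided that it was also given before observation ended. It adds: "Missing dates will not be replaced". Neither document defines a prior medication.

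SAP section 9.3 plans one medication summary for the safety population: "Incidences of prior and concomitant medications will be summarized by ATC level 2 and ATC level 4".

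Protocol section 4.2 begins "Details of relevant concomitant medications will be recorded in the CRF" and then lists the relevant drugs. One item on the list is "Pre-transfusion medications taken to prevent allergic reactions (including steroids").

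SAP section 5.2 allows event rates to be broken down by characteristics found on inspection of the data, with these examples: "particular indications for TPE, relevant concomitant medications, or SMQs covering a noticeable number of events". Protocol section 9.2.3 adds subgroup presentations by concomitant medication where appropriate.

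For exposure timing, Protocol section 5.4 says that "time details of each infusion episode will be recorded". The documents do not say whether medications get a clock time or only a date.

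**The concern.** Read as the only definition, the section 8.3 rule leaves two groups of drugs outside the concomitant class.

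- **Drugs whose timing cannot be established.** Blank dates are not filled, so these drugs cannot be shown to fall after the first infusion began. They cannot be shown to be prior either, and no class is named for them. If the case report form takes only a date (an assumption), a drug given only on the day of the first exchange could fall here even with a complete date.
- **Premedication given only before the first exchange.** The protocol counts it as relevant, but it fails the SAP test.

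This is a safety study. Protocol section 1.3 names pruritus and urticaria among the commonest reactions and reports hypersensitivity after marketing, so anti-allergic premedication is a covariate worth having right. If the label drove a breakdown of event rates, patients premedicated only before the first exchange would be counted as unexposed, and the contrast between the groups would shrink.

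**Working it through.** The plan states no figure on this point, so there is none to reproduce. The check has three parts: what the rule does, where its label is used, and how large an effect could be.

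**1. The rule by timing of the drug**

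| Timing | Result under SAP 8.3 |
|---|---|
| Shown to be given after the first infusion began and before observation ended | Concomitant |
| Premedication before a second or later exchange | Concomitant, because it falls after the first infusion began |
| Shown to be given only before the first infusion | Fails the test; presumably prior |
| Timing missing or too incomplete to decide | Fails the test; class not named |

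The last row does have a default in effect. Requiring proof of timing while leaving blank dates blank makes not concomitant the implied outcome. If the rule is instead read as a sufficient condition only, the default disappears, but premedication is then no longer excluded. The rule therefore cannot both lack a default and exclude premedication.

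**2. Where the label could matter**

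- *Primary endpoint.* SAP sections 3.2.1 and 11.1 count events per patient and per exchange. Medication class plays no part.
- *Medication summary.* SAP section 9.3 has one entry and one sentence covering both classes. In a joint table, a drug counted as prior rather than concomitant still appears.
- *Exploratory breakdowns.* SAP section 5.2 speaks of relevant concomitant medications, the term that Protocol section 4.2 defines by a list that includes premedication. No passage ties these breakdowns to the section 8.3 label.
- *Per-protocol set.* SAP sections 7 and 9.2 leave decisions on prohibited medication to a data review before database lock. The label does not decide them.

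**3. Size if a breakdown did use the label**

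The documents give no share of patients premedicated, none premedicated only before the first exchange, and none with undatable drugs. All shares and risks below are assumptions, for 40 patients.

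*Premedication.* Let E be the number premedicated, U = 40 − E the number not, and m the number premedicated only before the first exchange. If those m patients have the same risk as other premedicated patients,

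observed difference / true difference = U / (U + m).

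With E = 20, U = 20:

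- m = 5: 20/25 = 0.80
- m = 10: 20/30 = 0.67
- m = 15: 20/35 = 0.57

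For E from 12 to 28 and m from 25% to 75% of E, the factor runs from 28/31 = 0.90 down to 12/33 = 0.36.

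Worked case with E = 20, m = 10 and risks of 10% if premedicated and 30% if not:

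- true difference: 30% − 10% = 20 points
- rate in patients without the label: (20 × 0.30 + 10 × 0.10) / 30 = 7/30 = 23.3%
- observed difference: 23.3% − 10% = 13.3 points

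The exact 95% interval is 11.9% to 54.3% for 6/20 and 9.9% to 42.3% for 7/30. The shift from 30.0% to 23.3% lies well inside both.

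*Unknown timing.* Let k patients have a drug that cannot be placed, and let a share p of these truly overlap treatment. The present rule is wrong for k × p of them. The opposite rule, concomitant unless shown otherwise, is wrong for k × (1 − p). The two are equal at p = 0.5. With k = 4:

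| p | Present rule wrong | Opposite rule wrong |
|---|---|---|
| 0.25 | 1 | 3 |
| 0.50 | 2 | 2 |
| 0.75 | 3 | 1 |

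At the extremes of p, either rule is wrong for at most 4/40 = 10.0%.

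**The case for a change.** The strongest case for a change is that a safety study should lean towards showing possible exposure, whereas the implied default hides it. SAP section 8.3 also rules out any analysis of missing-data patterns, so no planned output would show how many drugs were affected. SAP section 8.4 lets further derived variables be settled in the programs, so the class could be chosen during programming. Because event rates are also given per exchange, a premedication indicator for each exchange would suit them better than one label per patient. The cost would be about five sentences and one derived variable.

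Part of this stands. The label prior should have been defined, the class for unknown timing is not named, and an indicator for each exchange would be more useful if premedication were examined.

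The rest does not carry a change. Preferring the opposite default is a trade-off that the documents cannot settle, since nothing indicates whether p exceeds one half. SAP section 8.4 already allows the indicator to be added and requires it to be documented, so its absence blocks nothing. Other provisions limit the problem:

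- Protocol section 6.1 has concomitant medication taken at screening, during each exchange, soon afterwards and at 24 hours, which helps to place drugs in time.
- Protocol section 8.1.3 requires discrepancies to be resolved before database lock.
- The patient profiles in SAP section 5.2 show interventions on a time scale for expert review.

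Queries cannot recover a clock time that was never asked for, but whether it was asked for cannot be judged from these documents.

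**Conclusion.** No change is needed. The wording gap is genuine but affects only labels: it could show in a medication table split into prior and concomitant drugs, or in an exploratory breakdown built on the section 8.3 label. The plan commits to neither. On the most natural reading, with a joint table and breakdowns based on the Protocol 4.2 list, the effect is zero. On the less favourable reading it cannot be sized from the documents, and under the assumed shares it is small against the uncertainty of rates in about 40 patients. SAP section 5.2 treats every interval as exploratory, and no pre-specified result depends on the label.

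This rests on two readings: that section 9.3 means a combined summary, and that relevant concomitant medications in section 5.2 carries the protocol's meaning. Both fit the text better than the alternatives. A statistician preparing the outputs would settle the meaning of prior and list the undatable drugs as a matter of routine.
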